11.1.3 Definition of Resolution of Thrombocytopenia

Resolution of Thrombocytopenia will be defined as:

- An increase in the platelet count to greater than $100 \times 10^3 / \mu\text{L}$ in patients with a nadir platelet count less than $100 \times 10^3 / \mu\text{L}$ or
- A stable, non-declining platelet count for more than 72 hours following the initiation of therapy in patients with a nadir platelet count greater than $100 \times 10^3 / \mu\text{L}$.

11.1.4 Definition of Recovery of Thrombocytopenia

Recovery of Thrombocytopenia will be defined as:

- An increase in platelet count to greater than $100 \times 10^3 / \mu\text{L}$ in patients with a pre-apixaban platelet count less than $100 \times 10^3 / \mu\text{L}$ or
- An increase in the platelet count to 1.5 times the pretreatment value in patients with a pre-apixaban platelet count greater than $100 \times 10^3 / \mu\text{L}$

12 DATA REPORTING / REGULATORY REQUIREMENTS

Adverse event lists, guidelines, and instructions for AE reporting can be found in Section 7.0

(Adverse Events: List and Reporting Requirements).

12.1 Data Reporting

12.1.1 Method

The Office of Data Quality (ODQ) will collect, manage, and perform quality checks on the data for this study.

12.1.2 Responsibility for Data Submission

Investigative sites within DF/HCC or DF/PCC are responsible for submitting data and/or data forms to the Office of Data Quality (ODQ) in accordance with DF/HCC policies.

12.2 Data Safety Monitoring

The DF/HCC Data and Safety Monitoring Committee (DSMC) will review and monitor toxicity and accrual data from this study. The committee is composed of medical oncologists, research nurses, pharmacists, and biostatisticians with direct experience in cancer clinical research. Information that raises any questions about participant safety will be addressed with the Overall PI and study team.

The DSMC will review each protocol up to four times a year or more often if required to review toxicity and accrual data. Information to be provided to the committee may include: up-to-date participant accrual; current dose level information; all grade 2 or higher unexpected adverse events that have been reported; summary of all deaths occurring within 30 days of intervention for Phase I or II protocols; audit results, and a summary provided by the study team. Other information (e.g. scans, laboratory values) will be provided upon request.

13 STATISTICAL CONSIDERATIONS

13.1 Study Design/Endpoints

This is a prospective, open label, single center study designed to evaluate the activity and tolerability of apixaban for the treatment of hospitalized patients with a confirmed diagnosis of isolated heparin induced thrombocytopenia (HIT).

Standard therapy with argatroban in isolated HIT has been associated with an estimated 6-8% incidence of new TEC (approximately 7%). However, the literature also reports mortality rates of up to 20% within 30 days of initiation of argatroban therapy. Furthermore, two recent “real world” analyses revealed a much higher risk of death, limb amputation and new thrombosis than was reported in prior studies.^{13,14}

The primary endpoint of this study is to evaluate the activity of the oral factor Xa inhibitor, apixaban as monotherapy in patients with heparin induced thrombocytopenia (HIT) and heparin

inducted thrombocytopenia with thrombosis (HITT), as defined by the incidence of new symptomatic thromboembolic complications (TEC) within 30 days of the time of initiation of apixaban.

The proportion of patients with confirmed HIT who are alive without new TEC at day 30 will be reported as a binomial proportion. We will also report the rate of new TEC, as estimated in the context of a cumulative incidence model in which death before day 30 in the absence of new TEC is treated as a competing risk.

Based on a recent “real world” analysis, where ¼ patients had HITT and ¾ patients had isolated HIT, the proportion of patients alive and without TEC was 59% in the HITT group and 66% in the isolated HIT group.¹⁴ We calculated the expected proportion of patients alive and without TEC for this present study based on the proportion of patients and event rates in each group from the real world analysis.

A total of 49 patients with a diagnosis or high clinical suspicion for HIT will be enrolled in this study using a one-stage design. We assume a conservative 10% frequency of negative confirmatory testing, thus yielding at least 44 patients with confirmed HIT in whom to assess the efficacy of this treatment at the conclusion of the trial. We anticipate that we will accrue and complete follow up on all patients within 2 years, based on investigators’ estimates of incident cases of HIT at MGH.

If at least 34 of 44 confirmed HIT patients are alive without new TEC at day 30, we will consider the study a success. The lower bound of the exact 90% confidence interval associated with this outcome is 0.65, suggesting that if we observe a 77% success rate, the probability that the true but unknown success rate is less than 65% is less than 0.05. We note again that in this calculation, both new TEC or death without TEC by day 30 are considered failures. We will also estimate the rate of new TEC at day 30 using the cumulative incidence model, and provide a 90% confidence interval based on the model estimate of variance.

A descriptive analysis of the secondary efficacy endpoints will be obtained.

Exact binomial 90% confidence intervals will be provided.

Demographic and baseline characteristics will be summarized overall using descriptive statistics (mean, median, standard deviation, minimum, and maximum) for continuous variables (e.g., age) and counts and percents for categorical variables (e.g., gender or race).

90% EXACT BINOMIAL CONFIDENCE INTERVALS FOR VARIOUS OBSERVED PROPORTIONS OF PATIENTS ALIVE WITHOUT NEW TEC AT DAY 30

Observed Response Rate	90% CI
-------------------------------	---------------

32/44 (73%)	(60% to 83%)
34/44 (77%)	(65% to 87%)
36/44 (82%)	(70% to 91%)

13.2 Sample Size, Accrual Rate and Study Duration:

See Section 13.1 above.

Both men and women of all races and ethnic groups are eligible for this trial. It is hoped that the accrual targets will resemble the gender, ethnic, and racial composition of the U.S. population as closely as possible.

13.3 Interim Monitoring Plan:

The study will be suspended for toxicity review if 5 or more patients out of the first 15 experience major hemorrhagic or thrombotic complications. The following table summarizes the probability of suspension given various probabilities of major hemorrhagic or thrombotic complications.

Probability of major hemorrhagic or thrombotic complications	0.13	0.20	0.33	0.40
Probability of suspension	0.04	0.16	0.60	0.78

Suspension will also be warranted if death without new TEC occurs in 2 or more of the first 15 patients. The following table summarizes the probability of suspension given various probabilities of death without new TEC.

Probability of death without new TEC	0.10	0.13	0.20	0.25
Probability of suspension	0.45	0.61	0.83	0.92

13.4 Analysis of Primary Endpoints:

See section 13.1

13.5 Analysis of Secondary Endpoints:

See section 13.1

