3.1 Eligibility Criteria

3.1.1 Hospitalized patients at MGH and participating Dana Farber/Harvard Cancer Center (DF/HCC) sites.

3.1.2 Patient must have a 4 T score of ≥ 5 as calculated by the following criteria:

- **Thrombocytopenia**
 - Platelet count fall >50 percent and nadir $\geq 20,000$ /microL – 2 points
 - Platelet count fall 30 to 50 percent or nadir 10 to 19,000/microL – 1 points
 - Platelet count fall <30 percent or nadir $<10,000$ /microL – 0 points
- **Timing of platelet count fall**
 - Clear onset between days 5 and 10 or platelet count fall at ≤ 1 day if prior heparin exposure within the last 30 days – 2 points
 - Consistent with fall at 5 to 10 days but unclear (eg, missing platelet counts), onset after day 10, or fall ≤ 1 day with prior heparin exposure within 30 to 100 days – 1 point
 - Platelet count fall at <4 days without recent exposure – 0 points
- **Thrombosis or other sequelae**
 - Confirmed new thrombosis, skin necrosis, or acute systemic reaction after intravenous unfractionated heparin bolus – 2 points
 - Progressive or recurrent thrombosis, non-necrotizing (erythematous) skin lesions, or suspected thrombosis that has not been proven – 1 point
 - None – 0 points
- **Other causes for thrombocytopenia**
 - None apparent – 2 points
 - Possible – 1 point
 - Definite – 0 points

3.1.3 Patient must meet one of the following:

- Have a confirmed diagnosis of HIT by Heparin-PF4 EIA or other accepted confirmatory test (serotonin-release assay, platelet aggregation assay).
- Have a high clinical suspicion of HIT (either Heparin-PF4 result is pending, or Heparin-PF4 result is negative or not obtained but a confirmatory test is pending)

Testing for HIT at MGH and participating DF/HCC sites is extremely reliable. MGH and participating DF/HCC sites currently use an extensively validated PF4-H IgG-based ELISA for HIT which has 94% specificity with a negative predictive value of 99.7% and a sensitivity that is close to 95%.

- 3.1.4 Patients can be treated with a non-heparin anticoagulant (such as argatroban, bivalirudin, or fondaparinux) for up to 7 days prior to enrollment.
- 3.1.5 Age 18 years or older.
- 3.1.6 ECOG performance status ≤ 2
- 3.1.7 Participants must have organ and marrow function as defined below:
- absolute neutrophil count $\geq 1,500/\text{mcL}$
 - AST(SGOT) and ALT(SGPT) $\leq 2.5 \times$ institutional upper limit of normal
 - creatinine clearance $\geq 25 \text{ mL/min}$ as was used in the AMPLIFY trial¹⁶

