5.10 Early Withdraw

Any patient who is enrolled in the study, but withdraws prematurely at any time for any reason before the end of their Day 30 follow-up visit (or phone call) for isolated HIT or Day 90 follow up visit (or phone call) for HITT, is considered an early withdraw and will not be replaced. A

complete set of data including the reason for the early withdraw will be collected on each patient through the time of withdraw. Every effort will be made to ascertain patient safety and survival information at the Day 30 follow-up time-point for isolated HIT and Day 90 for HITT.

Note: Date of follow up refers to the total days since initiation of treatment.

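### Section 13.1 states the expected number of confirmed patients (44 of 49) as a minimum, and the success rule is defined only for that one denominator

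*Combined protocol and SAP*

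**What the plan says.** Section 13.1 fixes the enrolment: "A total of 49 patients with a diagnosis or high clinical suspicion for HIT will be enrolled in this study using a one-stage design". It then derives the number available for the efficacy analysis: "We assume a conservative 10% frequency of negative confirmatory testing, thus yielding at least 44 patients with confirmed HIT". No source is given for the 10%.

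The success criterion follows in the same section: "If at least 34 of 44 confirmed HIT patients are alive without new TEC at day 30, we will consider the study a success". Its justification is that "The lower bound of the exact 90% confidence interval associated with this outcome is 0.65", and all three rows of the confidence-interval table in 13.1 use 44 as the denominator.

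Three other sections determine how many patients reach that analysis:

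- **Section 3.1.3** admits confirmed patients and also those under high clinical suspicion, described as "either Heparin-PF4 result is pending, or Heparin-PF4 result is negative or not obtained but a confirmatory test is pending". No limit on the number of such patients is stated. Section 3.1.2 applies to everyone: "Patient must have a 4 T score of ≥ 5 as calculated by the following criteria".
- **Section 13.6.2** places the primary efficacy analysis in the per-protocol set, which consists of dosed patients minus those later ruled out by a negative confirmatory test.
- **Section 5.10** says that a patient who withdraws early "is considered an early withdraw and will not be replaced". No section provides for replacing test-negative patients or for enrolling until 44 are confirmed.

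**The concern.** The confirmed count is random. Enrolment stops at 49 whatever the test results, some results arrive after entry, and negative ones remove patients from the primary analysis. A minimum would need a mechanism to enforce it, such as continued enrolment until 44 are confirmed. The plan has none.

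What is at stake is the decision rule more than precision. The plan defines success at one denominator, which will probably not be the one obtained. If the count is 42 or 46, the team must choose between keeping 34, scaling the proportion and recomputing a bound. These are different tests, and in an open-label single-arm trial the choice would be made with the outcomes already visible.

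**Working it through.** **Inputs.** Enrolment 49, negative rate 10%, success rule 34 of 44 and reference rate 0.65 with an exact 90% interval, all from 13.1. The observed rate that 13.1 attaches to success, 0.77, is used as an illustrative true rate.

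**Step 1: reproduce the plan's figures.** Inflating for negatives, 44 / 0.90 = 48.9, rounded up to 49. In reverse, 49 × 0.90 = 44.1. The exact (Clopper-Pearson) 90% interval for 34/44 is 0.645 to 0.871, matching the printed 65% to 87%. The plan's arithmetic is right for a mean yield.

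**Step 2: is 44 a minimum?** Let X be the number testing negative, X ~ Binomial(49, 0.10). At least 44 confirmed means X ≤ 5.

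| Confirmed patients | Probability at 10% negative |
|---|---|
| 44 or more | 0.635 |
| fewer than 44 | 0.365 |
| exactly 44 | 0.185 |
| 45 to 49 | 0.450 |
| 41 or more | 0.948 |

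**Step 3: sensitivity to the negative rate.** The rates other than 10% are assumptions, because the documents do not say what share of patients will enter unconfirmed.

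| Negative rate | Expected confirmed | P(44 or more) |
|---|---|---|
| 5% | 46.6 | 0.965 |
| 8% | 45.1 | 0.805 |
| 10% (plan) | 44.1 | 0.635 |
| 15% | 41.7 | 0.236 |
| 20% | 39.2 | 0.055 |

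With 49 enrolled, 90% assurance of 44 confirmed needs a negative rate of about 6.6% or lower.

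**Step 4: what happens if 34 is kept at another denominator.** The chance of declaring success is P(Y ≥ 34) with Y ~ Binomial(n, p).

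| Confirmed n | p = 0.65 | p = 0.77 |
|---|---|---|
| 40 | 0.004 | 0.155 |
| 42 | 0.019 | 0.346 |
| 44 | 0.057 | 0.567 |
| 46 | 0.132 | 0.755 |
| 49 | 0.315 | 0.921 |

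**Step 5: a rule defined at every count.** For each n, take the smallest number of successes whose exact 90% lower bound is at least 0.65, unrounded.

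| n | Successes needed | Lower bound | P(success) at 0.65 |
|---|---|---|---|
| 38 | 30 | 0.652 | 0.047 |
| 39 | 31 | 0.660 | 0.038 |
| 40 | 32 | 0.668 | 0.030 |
| 41 | 33 | 0.675 | 0.024 |
| 42 | 33 | 0.656 | 0.043 |
| 43 | 34 | 0.663 | 0.034 |
| 44 | 35 | 0.670 | 0.028 |
| 45 | 35 | 0.652 | 0.047 |
| 46 | 36 | 0.659 | 0.038 |
| 47 | 37 | 0.666 | 0.031 |
| 48 | 38 | 0.672 | 0.025 |
| 49 | 38 | 0.656 | 0.042 |

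At a 10% negative rate, counts of 38 to 49 cover probability 0.997. At n = 44 the unrounded bound needs 35 successes: 34 of 44 has a lower bound of 0.645 and a one-sided error of 0.057 at 0.65, so the statement in 13.1 that the probability is below 0.05 holds only for the rounded bound.

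**The case against.** The best defence is that the consequence for precision is minor. At the plan's rate the shortfall, if any, is usually one to three patients. The exact 90% interval is 0.226 wide at 34/44 and 0.232 wide at 32/41. A binomial proportion with an exact interval is defined at any n, and an analyst could infer the intended rule from the lower bound of 0.65. The point on precision stands. The point on the rule stands only in part: the inference is reasonable, but the plan does not make it, and rounding decides borderline cases. At 32/41 the lower bound is 0.648, which passes if rounded to 0.65 and fails if not.

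Four stronger readings are tempting, and the documents do not support them:

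- **Untested patients are admitted.** They are not. Section 3.1.3 requires a result to be pending, 5.3.1 makes a confirmatory test mandatory, and every patient needs a 4T score of at least 5. Such patients are unconfirmed at entry, not untested.
- **The 10% is too low.** Nothing shows this. The assay performance quoted in 3.1.3 would give an expected negative share only with the prevalence of HIT among pending entrants and the share entering pending, and the documents give neither.
- **Early withdrawals shrink the confirmed set further.** Under 13.6.2, a dosed patient with confirmed HIT who withdraws stays in the per-protocol set. Section 5.10 also calls for every effort to obtain safety and survival information at Day 30.
- **Unconfirmed entry should be capped.** A cap would not cure the problem. Results already pending can turn negative after it takes effect, and counts of 45 to 49 (probability 0.45) would still have no stated threshold. It would also change who enters and their prior anticoagulant exposure.

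**Conclusion.** The point holds as a mis-stated yield and an incomplete decision rule. It is not an error in the sample-size arithmetic. On the plan's own assumption, the stated minimum fails with probability 0.37, and the one denominator for which success is defined occurs with probability 0.18. Applying 34 unchanged would move the false-success probability at 0.65 from 0.004 with 40 confirmed patients to 0.132 with 46.

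The yield probabilities assume independent patients with a common 10% negative rate. The effect of keeping 34 at another denominator does not depend on that rate. The loss of precision at 10% negative is small and would not by itself justify enrolling more patients.

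**What to change.** 1. In 13.1, replace the minimum with an expectation: about 44 confirmed patients expected, with probability about 0.63 of 44 or more at a 10% negative rate.
2. In 13.1, state the success rule by the actual number confirmed, for example as the smallest count whose exact 90% lower bound is at least 0.65, and print the Step 5 table for 38 to 49 patients.
3. Say whether the bound is rounded. Unrounded, 44 patients require 35 successes. If 34 of 44 is to be kept, give the reference as 0.645 and amend the claim that the probability is below 0.05. With that reference, the table changes only at 41 (32 successes), 44 (34) and 48 (37).

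**Cost.** A slightly less favourable stated yield and one small table, with no extra patients and no change to eligibility. The unrounded rule is a little harder to meet: with 44 confirmed and a true rate of 0.77, the chance of success is 0.425 needing 35, against 0.567 needing 34.

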13.6.2 Evaluation of the Primary Efficacy Endpoint

The full analysis (FA) dataset will include all patients that receive at least one dose of study drug. The per protocol (PP) dataset is a subset of the FA dataset, excluding patients that are subsequently ruled out for this diagnosis by negative confirmatory laboratory testing. The primary efficacy analysis will be conducted in the PP data set. All safety analyses will be performed on the FA dataset. The incidence of new TEC following the initiation of apixaban therapy for HIT is the primary efficacy endpoint of this study, however the tolerability and side effects will be monitored as well.

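### The exact 90% lower bound for 34/44 is 0.6451, not 0.65, so the below-5% claim against 65% in Section 13.1 narrowly fails (exact tail 5.73%)

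*Combined protocol and SAP*

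**What the plan says.** Section 13.1 sets a count as the success rule: "If at least 34 of 44 confirmed HIT patients are alive without new TEC at day 30, we will consider the study a success". It supports that count with an interval statement, "The lower bound of the exact 90% confidence interval associated with this outcome is 0.65", and concludes that, on observing 77%, "the probability that the true but unknown success rate is less than 65% is less than 0.05". The table in the same section lists the interval for 34/44 as 65% to 87%, and the section says of its intervals generally: "Exact binomial 90% confidence intervals will be provided".

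On where the benchmark comes from, Section 13.1 cites a real-world analysis with a quarter of patients in the HITT group and three quarters with isolated HIT, in which "the proportion of patients alive and without TEC was 59% in the HITT group and 66% in the isolated HIT group". It then says "We calculated the expected proportion of patients alive and without TEC for this present study" from those shares and rates, but does not print the result.

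The 44 is a projection. From 49 enrolled, 10% are assumed to test negative, "thus yielding at least 44 patients with confirmed HIT". Section 13.6.2 runs the primary analysis in the per-protocol set, "excluding patients that are subsequently ruled out for this diagnosis by negative confirmatory laboratory testing", so the actual denominator may not be 44.

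**The concern.** A bound rounded to two decimals may be printed as 0.65, but it cannot then serve as a strict threshold at 65% unless the unrounded value is at or above 0.65. Here it is slightly below. The sentence that justifies the success rule therefore claims an error rate below 5% at a benchmark where the exact error is above 5%.

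This matters because the rule is the only formal success criterion in a single-arm study, and 34/44 is its boundary result. If exactly 34 of 44 were observed, a report giving the exact bound to three decimals would print 0.645. The study would be a declared success whose own interval includes the 65% that the plan says it excludes. Correcting the sentence after such a result would look post hoc.

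**Working it through.** **Inputs (all from Section 13.1).** Cut-off 34, n = 44, two-sided exact 90% interval (5% in each tail), named benchmark 65%, historical rates 59% (weight 1/4) and 66% (weight 3/4).

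**Step 1: reproduce the printed table.** The Clopper-Pearson lower limit for x of n is the 0.05 quantile of Beta(x, n − x + 1). The upper limit is the 0.95 quantile of Beta(x + 1, n − x).

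| Observed | Exact 90% interval | Printed in plan |
|---|---|---|
| 32/44 | 0.5959 to 0.8345 | 60% to 83% |
| 34/44 | 0.6451 to 0.8712 | 65% to 87% |
| 36/44 | 0.6958 to 0.9062 | 70% to 91% |

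All three rows reproduce after rounding to whole percent, which confirms the method. To five decimals the lower bound for 34/44 is 0.64505.

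**Step 2: test the claim at 65%.** The exact lower bound exceeds p0 only when P(X ≥ 34 | n = 44, p0) is below 0.05. At p0 = 0.65 this tail is 0.0573. That is above 0.05 by 0.0573 − 0.05 = 0.0073, or 0.7 percentage points.

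**Step 3: find where the claim holds.** The weighted historical rate is 0.25 × 0.59 + 0.75 × 0.66 = 0.6425. If each rate was rounded to whole percent, and the 1/4 and 3/4 shares are taken as exact, the weighted rate could be anywhere from 0.25 × 0.585 + 0.75 × 0.655 = 0.6375 to 0.25 × 0.595 + 0.75 × 0.665 = 0.6475.

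| Benchmark p0 | P(X ≥ 34 given n = 44, p0) |
|---|---|
| 63.75% | 4.03% |
| 64.25% | 4.65% |
| 64.5% | 4.99% |
| 64.75% | 5.35% |
| 65% | 5.73% |

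The claim is true up to about 64.5% and false at 65%. Against the weighted historical rate it is true on the rounded inputs, but not across the whole range that rounding allows.

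**Step 4: the next cut-off.** For 35/44 the exact 90% lower bound is 0.6702, and P(X ≥ 35 | n = 44, 0.65) = 0.0275. A strict below-5% rule at 65% therefore needs 35 successes.

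**Step 5: what one extra success costs.** The true rates here are assumptions; the plan states none.

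| Assumed true rate | P(X ≥ 34) | P(X ≥ 35) | P(X = 34) |
|---|---|---|---|
| 80% | 74.6% | 61.7% | 12.9% |
| 85% | 94.3% | 88.6% | 5.7% |

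The last column is the probability that the choice between 34 and 35 decides the outcome.

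**The case against.** The printed bound is not itself a mistake: 0.64505 rounds to 0.65. The operative rule is a count, and the 65% appears only in the explanation that follows. The plan states no formal null hypothesis and no type I error limit. On the printed historical inputs the natural benchmark is 64.25%, where the rule's error is 4.65%, so the design does what it appears to have been built to do. Read literally, the sentence is a probability about the true rate. A flat prior gives 4.7% for that, which is under 5%. Finally, a benchmark of 64.5% is fitted to the bound and has no source of its own.

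Much of this stands, and it is why the point is minor. The rounding is ordinary, the count is unaffected as written, and the success verdict changes only if the cut-off is raised to 35. It does not rescue the sentence. The plan names the exact interval, derives its claim from that interval and states no prior. The weighted rate is never printed, and rounding of its inputs leaves open whether 34/44 meets 5% against it. The one benchmark named in the justification is 65%, and there the claim is false. It is fair that 64.5% has no independent origin. It is offered as the figure the existing cut-off can support, and the weighted rate would be the more traceable choice if it were printed from source counts.

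**Conclusion.** The claim is wrong as written, by a small margin. Under the exact binomial method that the plan specifies, the lower bound for 34/44 is 0.6451 and the error of the rule at 65% is 5.73% rather than below 5%. The benchmark is overstated by about half a percentage point. The size of the error rests only on n = 44, the cut-off of 34 and the exact interval; no outside figure is needed. Sample size, conduct and the count of 34 are not affected. What fails is the stated justification of the success rule, and it would show only if the result fell exactly on the boundary.

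**What to change.** Rewrite the sentence in Section 13.1 so that success means the unrounded Clopper-Pearson 90% lower bound exceeds one stated benchmark, at the actual number of confirmed patients.

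- **Option A (preferred).** State the benchmark as 64.5% and keep 34/44; the error is 4.99%. The cost is a claim half a percentage point less favourable. There is no loss of power at n = 44.
- **Option B.** Keep 65% and require 35/44; the lower bound is 0.670 and the error 2.75%. The chance of declaring success falls from 74.6% to 61.7% at an assumed true rate of 80%, and from 94.3% to 88.6% at 85%.

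If the weighted historical rate is preferred as the benchmark, print it from unrounded source counts, because at 64.75% the 34/44 rule would again exceed 5% (5.35%).

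As an optional clarification, the same sentence settles the cut-off when the confirmed number is not 44:

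| Confirmed n | 40 | 41 | 42 | 43 | 44 | 45 | 46 | 47 | 48 | 49 |
|---|---|---|---|---|---|---|---|---|---|---|
| Cut-off at 64.5% | 32 | 32 | 33 | 34 | 34 | 35 | 36 | 37 | 37 | 38 |
| Cut-off at 65% | 32 | 33 | 33 | 34 | 35 | 35 | 36 | 37 | 38 | 38 |

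Neither option needs additional patients.

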13.6 Reporting and Exclusions

13.6.1 Evaluation of Toxicity

All participants will be evaluable for toxicity from the time of their first treatment.

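### Both suspension rules in 13.3 end at patient 15 of 49; carrying the bleeding/thrombosis rule forward at its own one-third fraction would improve detection of a high event rate at modest cost

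*Combined protocol and SAP*

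**What the plan says.** Section 13.3 (Interim Monitoring Plan) has two rules. The first: "The study will be suspended for toxicity review if 5 or more patients out of the first 15 experience major hemorrhagic or thrombotic complications". The second: "Suspension will also be warranted if death without new TEC occurs in 2 or more of the first 15 patients". Each comes with a table of operating characteristics. For the first rule the rows are "Probability of major hemorrhagic or thrombotic complications 0.13 0.20 0.33 0.40" and "Probability of suspension 0.04 0.16 0.60 0.78".

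Section 13.1 sets the size and form of the trial: "A total of 49 patients with a diagnosis or high clinical suspicion for HIT will be enrolled in this study using a one-stage design". Section 13.6.1 defines the safety population: "All participants will be evaluable for toxicity from the time of their first treatment". Up to 49 patients can therefore contribute safety events.

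Section 12.2 has the DSMC review toxicity and accrual at most quarterly, with additional reviews if needed, and gives no numeric threshold. Its list of what the committee may receive includes "all grade 2 or higher unexpected adverse events that have been reported" and deaths within 30 days. Sections 5.7 and 6 take an individual patient off protocol therapy for a new symptomatic TEC or a major bleed.

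**The concern.** The two rules use the first 15 patients and then lapse. The remaining 49 − 15 = 34 patients, 34/49 = 69% of planned enrolment, are treated without any count that obliges the study to pause. The off-therapy rules act on one patient at a time and cannot suspend the study.

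The DSMC provision does not clearly close the gap. It has no threshold, its adverse-event item is restricted to unexpected events, and many forms of bleeding are listed as expected toxicities in section 7.7. Running totals of major bleeding and new TEC, which are what the 13.3 rule counts, are not named.

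This matters more in a single-arm, open-label study, where no concurrent control would reveal an excess. Section 2.2 cites one case report of apixaban monotherapy in HIT, and section 6.1 says no specific antidote is available. If the first look is passed while the true rate is 33%, about 34 × 0.33 = 11 further events would be expected among the later patients with no boundary in force.

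**Working it through.** **Inputs.** Boundary of 5 or more events in 15, and true rates 0.13, 0.20, 0.33 and 0.40 (13.3); 49 enrolled (13.1); all treated patients count (13.6.1). A rate of 0.25 is added here to show the middle of the range.

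**Step 1: reproduce the plan's table.** P(suspend) = P(X ≥ 5), with X ~ Binomial(15, p).

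| True rate | Plan | Recomputed |
|---|---|---|
| 0.13 | 0.04 | 0.036 |
| 0.20 | 0.16 | 0.164 |
| 0.33 | 0.60 | 0.585 |
| 0.40 | 0.78 | 0.783 |

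The small difference at 0.33 is rounding of the rate: p = 1/3 gives 0.596, and p = 2/15 gives 0.040. The death table also reproduces. P(Y ≥ 2) in 15 is 0.451, 0.599, 0.833 and 0.920 at 0.10, 0.13, 0.20 and 0.25, against 0.45, 0.61, 0.83 and 0.92 in the plan; at 2/15 the second value is 0.613.

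**Step 2: carry the fraction forward.** The plan's boundary is 5/15 = 1/3. The same fraction gives 10/30 and 15/45. Let f(n, k) be the probability of k events in n patients with no suspension so far. Then f(n, k) = p·f(n−1, k−1) + (1−p)·f(n−1, k). At each look, the probability at or above the boundary is counted as suspension and removed.

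| True rate | 5/15 only | plus 10/30 | plus 10/30 and 15/45 |
|---|---|---|---|
| 0.13 | 0.036 | 0.037 | 0.037 |
| 0.20 | 0.164 | 0.181 | 0.185 |
| 0.25 | 0.314 | 0.363 | 0.381 |
| 0.33 | 0.585 | 0.690 | 0.741 |
| 0.40 | 0.783 | 0.888 | 0.932 |

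The probability of never suspending falls from 1 − 0.585 = 0.415 to 1 − 0.741 = 0.259 at 33%, and from 0.217 to 0.068 at 40%.

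**Step 3: expected enrolment at a 33% rate.** This is the number enrolled at suspension or completion.
- Current rule: 15 × 0.5852 + 49 × 0.4148 = 29.1.
- With both added looks, suspension occurs at 15, 30 and 45 with probabilities 0.5852, 0.1052 and 0.0506: 15 × 0.5852 + 30 × 0.1052 + 45 × 0.0506 + 49 × 0.2590 = 26.9.
- With 10/30 alone: 15 × 0.5852 + 30 × 0.1052 + 49 × 0.3096 = 27.1.

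**Step 4: tighter looks, for comparison.** Boundaries of 9/30 (30%) and 11/40 (27.5%) give 0.045, 0.260, 0.520, 0.862 and 0.975 at 0.13, 0.20, 0.25, 0.33 and 0.40. Expected enrolment at 33% is 24.8. Detection is higher, but suspension at 20% rises by 9.6 points and at 25% by about 21 points over the current rule.

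All figures assume that each patient's outcome is known at the look and that patients are independent with a common rate.

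**The case against.** An early look followed by periodic DSMC review is a legitimate choice for a small trial of a marketed drug at its approved VTE regimen. Crossing the boundary triggers a review, not termination. The death rule runs on the same 15 patients, so the chance that at least one rule suspends the study is no lower than the figures above. The practical saving is small: about two patients in expectation at 33%. The 45-patient look comes with only four left to enrol, and the 30-day outcome lag delays action under any rule. All of this stands, and it makes the point an improvement rather than a defect in the main analysis.

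Four stronger readings are tempting and not supported:

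- *Nobody monitors safety after patient 15.* DSMC review continues. Section 11.1.2 keeps TEC and major bleeding under observation throughout, and sections 7.9 to 7.11 route serious events to the overall investigator, the drug supplier, the IRB and the FDA. What ends is the numeric boundary.
- *The DSMC would not see these events.* The list in 12.2 is illustrative, allows a study-team summary and further data on request, and covers 30-day deaths. Its restriction to unexpected events would not clearly exclude new TEC, which is not in the expected list of 7.7. Intracranial and retroperitoneal bleeding are not named there either. The documents support only that cumulative counts are not named.
- *An extension costs almost nothing, however it is set.* That holds at 13%. At 20% and 25% the cost depends on the boundary, and 9/30 with 11/40 is a tighter rule than the plan's, not a continuation of it.
- *33% is by definition unsafe, or 13% acceptable.* The plan labels neither.

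**Conclusion.** The point holds as a cheap and worthwhile improvement. Both rules in 13.3 cover 15 of 49 patients, and no numeric study-level boundary applies to the other 34. Extending the bleeding/thrombosis rule at the plan's own fraction raises the chance of suspension by 15.6 points at 33% and 14.9 points at 40%. At lower rates the increase is 0.1 points at 13%, 2.1 at 20% and 6.8 at 25%. The 30-patient look alone gives 10.5 of the 15.6 points at 33%.

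Whether the extra suspensions at 20% to 25% count as false alarms or as wanted detections depends on an acceptable rate that the documents do not give. The figures also rest on outcomes being known at each look. The primary efficacy analysis and its success criterion are not affected.

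**What to change.** In 13.3:
- Carry the bleeding/thrombosis rule forward at one-third, for example suspension for toxicity review also at 10 or more of the first 30 and 15 or more of the first 45 treated patients, and replace the table with one for the full sequence.
- State which rate of major bleeding or thrombosis the sponsor regards as acceptable and which would be of concern. If tighter looks are preferred, the choice can then be justified against those rates, with the cost at 20% to 25% shown.
- Say explicitly that the death rule has the same first-15 limit, and whether that is intended.

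In 12.2, add cumulative counts of major bleeding and new TEC, with the number treated, to every DSMC package.

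The cost is one paragraph, one table and one line, using data already collected. The price in conduct is a somewhat higher chance of a pause at intermediate rates: about 2 points at 20% and 7 points at 25%.
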